## 9.8. Treatment After End of Study

After the end of the study, each subject will be treated according to standard clinical practice.

## 9.9. Dispensing and Storage

The IP supplied by [REDACTED] is to be used exclusively in the clinical study according to the instructions of this protocol. The Investigator is responsible for dispensing the IP according to the dosage scheme and for ensuring proper storage of the IP.

The Investigator must confirm the receipt of the IP.

### 9.9.1 Dispensing

At each visit from Visit 2 (Baseline) through the final monthly visit (Visit 13), subjects will be dispensed a monthly kit containing a sufficient number of PH94B Nasal Spray vials from the respective clinical site. Each study site will be provided with an appropriate supply of IP, and each vial will be individually numbered with a unique identification code.

Prior to the subject receiving the IP at each in-clinic visit, the Investigator or study staff will use a vial from their assigned kit to instruct the subject on how to ensure the IP is primed before use according to instruction. At least 1 vial of the IP will be primed at each clinic visit following Visit 2 (Baseline) as needed. The IP will be weighed prior to priming, and again when returned to study staff. Once primed the IP must be stored at room temperature.

Subjects should use a fresh vial at the start of each week. Subjects will be instructed to remove the new vial from their home refrigerator, bring it to room temperature and prime the spray actuator before use as needed. The clinic will dispense a kit of vials with unique serialized vial identification codes at each visit.

If the IP supply is lost or depleted prior to next in-clinic visit, subjects may notify the study site through the provided study site phone number to secure additional supply of IP.

### **9.9.2 Storage**

All IP supplied to each site by the sponsor will be maintained in a safe and secure (locked) area, stored upright in a refrigerator between 2°C (36°F) and 8°C (46°F), until dispensed, and away from direct sunlight and ultraviolet light. Access should be restricted to the designated responsible member(s) of the Investigator's staff and to the clinical monitor. The Investigator agrees that neither he/she nor any of the study staff will supply IP to any person other than subjects enrolled in the study.

Secure access to the storage area is the responsibility of the Investigator and designated staff.

New (unused) IP should be stored in the refrigerator. The spray actuator of the IP should be primed before use according to the instructions provided.

### **9.10. Drug Accountability**

Upon receipt of each IP shipment, an inventory must be performed, and a drug receipt log filled out and signed by the person accepting the shipment. The IP will be provided with each vial assembled individually to its spray actuator. It is important that the designated study staff count and verify that the shipment contains all the items noted in the shipment inventory. Any damaged or unusable IP in each shipment (active drug) will be documented in the study files.

Current and accurate inventory and dispensing records will be kept for all IP. Upon study completion a final inventory of all clinical supplies will be compiled. The Investigator or an assistant will instruct subjects to return spray vials to the clinical site, whether empty or containing unused IP, at study visits prior to subjects receiving additional supplies of IP. A copy of the Drug Receipt Form and the Drug Accountability Form will be retained in the Investigator's files.

If the subject reports the IP as being lost or stolen this will be recorded in the eCRF.

### **9.11. Labeling and Packaging**

Labeling and packaging of the IP will be performed by [REDACTED]

#### **9.11.1 Labeling**

The vials will have a label affixed that meets the applicable regulatory requirements and may include the following: IP name, dosage strength, lot number, protocol number, specified volume of contents, caution statement ("New Drug – Limited by United States Law to Investigational Use" and "Keep out of reach of children"), storage information, vial identification code, and the sponsor's name.

The vial identification codes will be recorded in the drug dispensing record and the eCRF.

Investigators must save all empty packaging or packaging containing unused vials for final disposition by the sponsor or contract pharmacy.

### **9.11.2 Packaging**

PH94B will be supplied in subject kits containing a sufficient number of individual PH94B Nasal Spray dosage units.

PH94B Nasal Spray dosage units are not childproof and should be stored out of reach of children.

## 10. STUDY PROCEDURES

Subjects must provide written informed consent for the present study before any study-related procedures are initiated, including the cessation of prohibited concomitant therapy.

The required safety and tolerability endpoints for subject evaluation are outlined in Section 13.1.4, with a comprehensive schedule of events in [Table 2-1](#). Every effort should be made to complete all required procedures and evaluations at the designated visits. A trained designated rater must see the subject at every visit. If available, the rater should be the same for a subject for each visit from Visit 2 (Baseline) to Visit 14, however, all raters will be trained for consistency.

Throughout the study, every reasonable effort should be made by study personnel to follow the timing of assessments and procedures in the schedule of events for each subject. If a subject misses a study visit for any reason, the visit should be rescheduled as soon as possible.

Subjects who have participated in a previous PH94B SAD study will be enrolled in this study and attend Visit 1 or Visit 2 depending on the interval since they finished participation in their antecedent study, as follows:

>14 Days Since Antecedent Study: Subjects who finished participation in their antecedent PH94B SAD study more than 14 days before entering the present study will attend Visit 1 of the long-term safety study and complete all necessary screening assessments as shown in the schedule of events ([Table 2-1](#)).

**For the purposes of enrollment, these subjects are referred to as “New Subjects”.**

<14 Days Since Antecedent Study: Subjects who enter the present study within 14 days after finishing participation in their antecedent PH94B SAD study without meeting any of the exclusion criteria of this long-term safety study will enter the present study at Visit 2 (see [Table 2-1](#)).

**For the purposes of enrollment, these subjects are referred to as “Completers”.**

- While these subjects enter the long-term safety study at Visit 2, Investigators must transcribe the following screening data (Visit 1) from the antecedent study to the present long-term safety study: demographics, the MINI, medical and psychiatric history, and the SAD Diagnostic Criteria checklist. If there have been any changes, these details should be updated. This data from the antecedent study must be re-entered into the [Visit 1 eCRF](#) for the present study. All other assessments scheduled for Visit 2 must be performed as indicated in the schedule of events (see [Table 2-1](#)).
- If the subject enters the present study on the same day as the last visit of their antecedent study, results from the assessments on that day may be used to enter data into the eCRFs for the antecedent study and for Visit 2 of the present study without repeating them.
  - For example, [REDACTED] assessment completed for the last visit of the antecedent study may be transcribed for this long-term safety study provided that the last visit occurred on the same day as Visit 2 for the present study. Details on preparing a certified copy of the results will be provided in the eCRF completion guidelines.

- For clinical laboratory assessments, 2 sets of blood and urine samples should be obtained and sent to the lab for analysis: one for the antecedent study and one for the long-term study. Note that these can be collected at the same time to avoid unnecessary needlesticks.

Subjects who have not participated in a prior PH94B SAD study may be permitted to enroll following approval by the sponsor on a case-by-case basis. For the purposes of enrollment, these subjects are referred to as “New Subjects”.

## 10.1. Study Duration

The study comprises a 7- to 35-day screening period and a treatment period of up to 12 months, and a follow-up visit at 2 weeks after the last visit.

## 10.2. Study Periods and Visits

A comprehensive schedule of study assessments is presented in [Table 2-1](#) and described in the following sections. Every effort should be made to complete all required procedures and evaluations at the designated visits. A window of  $\pm 3$  days is permitted for Visit 3 and the follow-up visit (Visit 15), with a window of  $\pm 7$  days permitted for Visits 4 through 13, and  $\pm 2$  weeks for Visit 14.

### 10.2.1 Screening and Washout

#### 10.2.1.1 Screening (Visit 1)

Screening begins after written informed consent has been obtained. The purpose of the screening phase is to:

- Ensure that appropriate subjects are entered into the study
- Determine that the subject meets all eligibility criteria
  - Subjects who enter this study more than 14 days after finishing participation in their antecedent study must undergo all the screening procedures at Visit 1 to ensure they meet eligibility
- Collect demographic and medical data permitting characterization of the subject

To meet these objectives, the duration of screening must be tailored to the individual subject and may last from a minimum of 7 to a maximum of 35 days. Subjects continuing to meet all eligibility requirements at Visit 2 (Baseline) will undergo treatment with IP (PH94B) up to Visit 14.

Generally, subjects who have participated in an antecedent PH94B SAD study will be informed about the study, the IP, required visits and scheduling, and asked whether they wish to participate. All subjects agreeing to participate must give written informed consent using the IRB-approved ICF before any study-related procedures are performed (including tapering of prohibited medications, see [Section 9.7.2](#)). The ICF will be signed and dated by the subject and Investigator or other appropriate site staff, and a copy of the signed ICF will be given to the subject. The informed consent process will be documented in the source records for each subject.

After the informed consent process is complete, the signed ICF will be obtained, and the Screening visit (Visit 1) occurs.

The following numbered procedures should be performed in a block fashion as per the order indicated. Assessments within a block, except for the first block, may be conducted in any order as per clinical judgement at Screening, which is to occur at least 7 days, but no more than 35 days prior to Visit 2:

1. ICF will be reviewed and completed before any other assessments. Collect demographic information; and assign subject number.
2. Urine sample for drug screen and pregnancy test (if appropriate) will be collected early in the screening visit to determine eligibility and to guide diagnostic interviews, especially with regards to substance use assessment. The urine sampling is to include:
  - a. Obtain urine sample for urine drug screen (UDS): Instant Exam to be performed on site, with results thoroughly documented in the source; urine sample to be sent to central laboratory for confirmation if on-site UDS is positive [REDACTED]  
[REDACTED].
  - b. For females of child-bearing potential, obtain urine sample and complete on-site urine pregnancy test.
3. Medical and psychiatric history and diagnosis (usually starting with MINI) to include:
  - a. Administer MINI (7.0.2).
  - b. Obtain medical history (including nicotine, alcohol use, and menstrual information on women of childbearing potential) and psychiatric history.
  - c. Record prior and concomitant treatment and medication use (medication name, dose, and frequency).
  - d. Complete SAD diagnostic criteria checklist.
4. Standardized assessments (usually starting with LSAS but per investigator judgement based on the MINI) to include:
  - a. Administer LSAS.
  - b. Administer HAM-D17.
  - c. [REDACTED]
  - d. Administer C-SSRS (Baseline).
  - e. Complete CGI-S with a recall period of 1 week (by the trained clinician).

5. Physical assessments (recommend blood draw last to avoid any potential impact on vitals and ECG assessment) to include:

- a. Perform physical examination, including height (inches) and body weight (pounds).  
The physical examination includes a review of the nasal passages. If total anosmia is suspected, Quick Olfactory Test (QOT) is to be administered.
- b. Measure vital signs after the subject has rested for 5 minutes: seated systolic and diastolic blood pressure, heart rate, respiratory rate, and body temperature (°F).
- c. Obtain 12-lead ECG in supine position after the subject has rested for 5 minutes.
- d. Obtain blood and urine samples for evaluation by the central clinical laboratory, including hematology, chemistry, thyroid functioning, and urinalysis (refer to Section 10.3.1.1.1 for complete list).

6. After these assessments are complete, review all inclusion and exclusion criteria.

Procedures for rescreening subjects who initially fail to meet study entry criteria are described in Section 14.3.

### **10.2.1.2 Washout Period**

In accordance with the study entry criteria (Section 8.2), the use of certain psychotropic medications, anxiolytics, or other preparations for the treatment of anxiety or social anxiety is prohibited within 30 days before study entry (considered as Visit 2, Baseline).

Where washout of prohibited medications (see Section 9.7.2) is required before Visit 2 (Baseline), tapering rates are at the discretion of the Investigator and are to be determined on an individual basis, with consideration to subject state, dose, and known pharmacokinetics of the medication being discontinued. The subject must be consented before any tapering is started.

### **10.2.2 Treatment Period**

#### **10.2.2.1 Visit 2 (Baseline)**

Subjects entering the study within 14 days of their antecedent PH94B SAD study will enter this study at Visit 2. These subjects will sign an ICF for the present study at this visit and complete all Visit 2 assessments as noted in the schedule of events (Table 2-1) and detailed in this section.

All subjects will complete the following Visit 2 assessments:

- Obtain urine sample for urine drug screen: Instant Exam to be performed on site, with results thoroughly documented in the source; urine samples will be sent to the central laboratory for confirmation as needed if on-site urine drug screen is positive. If the central laboratory urine drug screen result is positive [REDACTED]

[REDACTED], the subject may have to be excluded from the study; the Medical Monitor should be consulted on these cases

- For females of childbearing potential, obtain urine sample and complete on-site urine pregnancy test
- Record concomitant medication use
- Perform physical examination, including body weight (pounds). The physical examination includes a review of the nasal passages
- Measure vital signs after the subject has rested for 5 minutes: seated systolic and diastolic blood pressure, heart rate, respiratory rate, and body temperature (°F)
- Obtain 12-lead ECG in supine position after the subject has rested for 5 minutes
- Obtain blood and urine samples for evaluation by the central clinical laboratory, including hematology, chemistry, thyroid functioning, and urinalysis
- Review all inclusion and exclusion criteria

For subjects meeting all study inclusion criteria and no study exclusion criteria, the following Visit 2 procedures will be performed:

- Administer the LSAS
- Administer the HAM-D17
- [REDACTED]
- Administer the C-SSRS (Since Last Visit)
- Complete the CGI-S with a recall period of 1 week (by the trained clinician)
- Train subjects on the use, dosing, and storage of IP. The subject will be given instructions on:
  - how to position the actuator nozzle in the nasal passages and self-administer IP
  - the number of sprays per nostril per dose (1 per nostril)
  - how to store the nasal spray
  - Treatment with PH94B should be self-administered approximately 15 minutes prior to or during an anxiety-provoking social situation or event. [REDACTED]  
[REDACTED], with no more than 4 administrations per day. Treatment does not need to be administered every day.

- Train subjects on how to record study drug use on the eDiary application (see Study Procedures Manual for training on the eDiary application)
- Record any AEs

All prior, ongoing, or resolved AEs reported by subjects at the time of study entry will be considered as medical history during this study. Adverse events that become aggravated, accelerated, or exacerbated will be reported and considered as new AEs. Adverse events that recur will be considered as new AEs during this study.

- Dispense IP to subjects (1-month supply)

Subjects will be instructed to call a designated phone number provided by the study site to report any unusual or severe AEs or hospitalizations that may occur in between in-clinic visits.

Visit 3 will be scheduled 30 days ( $\pm 3$  days) from Baseline (Visit 2) for subjects.

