- c Physical examination will include measurement of weight and an examination of the nasal passages. Height will be measured at Screening and at Visit 14. The physical examinations done at Visit 1, Visit 2 and Visit 14 will be comprehensive. The physical examinations done at Visit 3 to Visit 13 will be focused but must include examination of the nasal passages and oropharynx. Other organ systems should be examined at Visit 3 to Visit 13 if the subject reports AEs or if the investigator has specific concerns.
- d [REDACTED].
- e 12-Lead electrocardiograms will be administered in a supine position after the subject has rested for 5 minutes.
- f For all subjects, a review of inclusion and exclusion criteria will be conducted at Visit 2 to confirm eligibility.

Note: Long-term C-SSRS will be administered at screening. All other C-SSRS evaluations will be "Since Last Visit."

Note: If central laboratory urine drug screen testing is positive for a subject [REDACTED], then the participation of the subject in the study may have to be discontinued. The Medical Monitor should be consulted on these cases. An unscheduled repeat urine drug screen may be obtained to investigate whether drug use is continuing.

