#### 8.2.1 Inclusion Criteria

To be considered eligible to participate in the study, all subjects must meet the following inclusion criteria:

1. Subject must have participated in a previous PH94B SAD study.  
Note: Subjects who have not participated in a prior PH94B SAD study may be permitted to enroll following approval by the sponsor on a case-by-case basis.
2. Written informed consent provided prior to conducting any study-specific assessment.
3. Male and female adults, 18 through 65 years of age, inclusive.
4. Women of childbearing potential must be able to commit to the consistent and correct use of an effective method of birth control throughout the study and must also have a negative urine pregnancy test result at both Screening (Visit 1) (for subjects who attend Visit 1) and Baseline (Visit 2), prior to IP administration. Effective methods of contraception include: condoms with spermicide, diaphragm with spermicide, hormonal contraceptive agents (oral, transdermal, or injectable), or implantable contraceptive devices.
5. Current diagnosis of SAD as defined in the Diagnostic and Statistical Manual of Mental Disorders, 5th Edition, and confirmed by the Mini-International Neuropsychiatric Interview (MINI).
6. Clinician-rated HAM-D17 total score < 18 at study entry (Screening [Visit 1] or Visit 2 [Baseline] as applicable).
7. Negative COVID-19 test for subjects with COVID-19 symptoms or those who had direct exposure to someone with a positive COVID-19 test, and/or completion of quarantine period consistent with requirements at the study site as determined by the investigator.

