#### 8.2.2 Exclusion Criteria

To be considered eligible for entry into the study, a subject must not meet any of the following exclusion criteria at study entry.

1. Any history of bipolar disorder (I or II), schizophrenia, schizoaffective disorder, psychosis, anorexia or bulimia, premenstrual dysphoric disorder, autism-spectrum disorder, obsessive-compulsive disorder, or treatment-refractory major depressive disorder.

Any other current Axis I disorder, other than SAD, which is the primary focus of treatment. Note that subjects with concurrent Generalized Anxiety Disorder are eligible for the study provided that Generalized Anxiety Disorder is not the primary diagnosis.

2. In the opinion of the Investigator, the subject has a significant risk for suicidal behavior during the course of their participation in the study, or
  - a. At Screening (for subjects who attend Visit 1): the subject scores “yes” on items 4 or 5 in the Suicidal Ideation section of the Columbia-Suicide Severity Rating Scale (C-SSRS) with reference to a 6-month period prior to screening; or
  - b. At Screening (for subjects who attend Visit 1): the subject has had 1 or more suicidal attempts with reference to a 2-year period prior to screening; or
  - c. At Baseline (Visit 2): the subject scores “yes” on items 4 or 5 in the Suicidal Ideation section of the C-SSRS with reference to last visit; or
  - d. The subject is considered to be an imminent danger to themselves or others.
3. Subjects using the following psychotropic medications at enrollment or within 30 days before study entry: antidepressants (including monoamine oxidase [MAO] inhibitors), anxiolytics, stimulants, anticonvulsants, mood stabilizers, antipsychotic medications, gabapentin, pregabalin, opioids, naltrexone, esketamine, and ketamine. Eszopiclone, ramelteon, melatonin, zaleplon, zolpidem, or anti-histamines prescribed for insomnia are allowed.
4. Use of benzodiazepines or unapproved treatments such as beta blockers, within 30 days before study entry and during the study. Use of beta blockers for treatment of hypertension or cardiac conditions is allowed. Subjects who have been taking benzodiazepines daily for 1 month or longer at the time of Visit 1 are not eligible to participate.
5. Use of any over-the-counter product or herbal preparation for treatment of the symptoms of anxiety or social anxiety within 30 days before study entry; concomitant use is prohibited during the study.

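### Protocol Section 10.2.2.1 gives the Visit 2 C-SSRS and HAM-D17 only after the criteria review and only to subjects who pass it, although the review depends on their results

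*Protocol*

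**What the plan says.** **Visit 2 procedures (Protocol 10.2.2.1).** The list has two parts. The first, for all subjects, covers the urine drug screen, pregnancy test, concomitant medication, physical examination, vital signs, ECG and laboratory samples. It ends with "Review all inclusion and exclusion criteria". The second part begins "For subjects meeting all study inclusion criteria and no study exclusion criteria, the following Visit 2 procedures will be performed" and contains LSAS, HAM-D17, C-SSRS, CGI-S, training, AE recording and dispensing, in that order.

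**Criteria that use these scales (Protocol 8.2).** Exclusion 2c applies at Baseline (Visit 2) to a positive answer on item 4 or 5 "in the Suicidal Ideation section of the C-SSRS with reference to last visit". It is not restricted by entry route. Inclusion 6 reads "Clinician-rated HAM-D17 total score < 18 at study entry (Screening [Visit 1] or Visit 2 [Baseline] as applicable".

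**Purpose of the Visit 2 review (Table 2-1, footnote f).** "For all subjects, a review of inclusion and exclusion criteria will be conducted at Visit 2 to confirm eligibility".

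**Order at Visit 1 (Protocol 10.2.1.1).** The scales are in block 4. Step 6 is "After these assessments are complete, review all inclusion and exclusion criteria".

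**Entry route (Protocol 7.1 and 10).** Subjects who finished their antecedent study within 14 days enter at Visit 2 and have no Visit 1 in this study.

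**The concern.** An eligibility review can apply only the results it has. At Visit 2 the written gate asks the site to decide that all criteria are met before two of the instruments that test them are given. It then gives those instruments only to subjects who have passed.

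The two criteria concern suicidal ideation and depression. Section 6.1 of the protocol also names suicidality and level of depression in the primary safety objective. If the text is followed literally, eligibility is recorded while exclusion 2c, and for some subjects inclusion 6, is still untested. If Table 2-1 is followed instead, the scales come first. With approximately 40 sites planned (Section 7.4), two readings of one visit make uneven practice and avoidable eligibility deviations likely.

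**Working it through.** No arithmetic applies and the plan gives no figure to reproduce. The check sets the passages side by side and follows each entry route through the Visit 2 text.

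| Source | Scales relative to the criteria review at that visit | Who is given them |
|---|---|---|
| 10.2.2.1, Visit 2 | After the review | Only subjects already meeting all criteria |
| Table 2-1, row order | LSAS, HAM-D17 and C-SSRS rows above the review row; CGI-S row below | No such restriction |
| 7.1, Visit 2 | Order not stated | All subjects |
| 10.2.1.1, Visit 1 | Before the review (block 4, then step 6) | Subjects being screened |

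The visit marks in the HAM-D17 row of Table 2-1 are blacked out in the public copy. The position of the row is visible, and Section 7.1 confirms that HAM-D17 is given at Visit 2.

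**Route A: subject who attended Visit 1.**
1. Inclusion 6 can be judged from the Visit 1 HAM-D17.
2. Exclusion 2c needs the Visit 2 C-SSRS.
3. Section 10.2.2.1 gives that C-SSRS only to subjects already found to meet no exclusion criterion.
4. The rule is circular for the C-SSRS only.

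**Route B: subject who enters at Visit 2.**
1. Section 10 lists the antecedent data to be transcribed: demographics, MINI, medical and psychiatric history, and the SAD checklist. Neither HAM-D17 nor C-SSRS is on that list.
2. Inclusion 6 therefore needs the Visit 2 HAM-D17. Exclusions 2a and 2b apply only to subjects who attend Visit 1, so 2c is the only exclusion scored from a C-SSRS result.
3. Both scales are behind the gate.
4. The rule is circular for both scales.

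**Exception within Route B.** Section 10 lets results from the last antecedent visit serve as Visit 2 data if both fall on the same day. Such a subject may have scores available at the review, provided the antecedent visit included the scales. The documents here do not show whether it did.

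**After the gate.** In the second block HAM-D17 and C-SSRS come before training, and dispensing comes last. No step there returns to the criteria once the scores are known.

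**Footnote f.** It makes the Visit 2 review the step that confirms eligibility for all subjects. The review as placed in 10.2.2.1 cannot do this for exclusion 2c, or for inclusion 6 in Route B, apart from the same-day exception.

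**The case against.** The strongest reply is that the binding rules are elsewhere and remain intact. Section 8.2 says that subjects who do not meet every criterion are not enrolled. Section 10.2.1.1 limits treatment to those still eligible at Visit 2. Exclusion 2c names the Visit 2 C-SSRS outright, and the opening of exclusion 2, with 2d, leaves room for the investigator's judgement. Both scores are in hand before any drug is handed over. Section 10.2.2.1 itself tells direct entrants to complete all Visit 2 assessments in the schedule. On this view a sensible site would act on a disqualifying score.

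Most of this stands, and it rules out the strongest inference. A reader might conclude that the protocol allows a subject with a positive item 4 or 5, or a HAM-D17 of 18 or more, to be enrolled and sent home with drug. It does not: dispensing in that situation would breach Section 8.2.

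It is also fair to say that Visit 2, unlike Visit 1, does not instruct sites to follow the listed order, and that a different order at another visit is a contrast and not a contradiction. But the problem does not rest on bullet order. The conditional sentence makes passing the review a condition for being given the scales. The instruction to direct entrants, like Section 7.1, conflicts with that sentence without removing it.

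A reader might also infer that depression present at entry would be counted as an on-study change. The documents do not support this. SAP Section 6.1.1 takes the HAM-D baseline from Visit 2, and under protocol Section 11.1.5 an event that began before treatment is treatment-emergent only if it worsens in severity or relationship once treatment starts.

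**Conclusion.** The point holds as an internal contradiction that leaves the written Visit 2 eligibility check unworkable for exclusion 2c in every subject and for inclusion 6 in subjects who enter at Visit 2, in both cases unless same-day antecedent results are used. It does not hold for HAM-D17 in subjects who attended Visit 1, because their Visit 1 score serves.

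The effect is on conduct: eligibility can be recorded before two safety-related criteria have been tested, and nothing in 10.2.2.1 sends the site back to the criteria before dispensing. It has no bearing on sample size or error rates.

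A reader might want a head count and multiply an assumed rollover share by the ceiling of 600 subjects. The documents state no such share, and they do not say how many rollovers would use same-day results, so no count is given here.

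The conclusion rests on the current protocol text. No blacked-out passage explains it, and it does not depend on the amendment log. It goes beyond a clerical slip because the gate changes who is assessed and what the review can use.

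**What to change.** Reconcile Sections 10.2.2.1, 8.2 and 7.1 and Table 2-1 by re-ordering Visit 2:

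- Move "Administer the HAM-D17" and the C-SSRS (Since Last Visit) line into the all-subjects block, above "Review all inclusion and exclusion criteria".
- Keep training and dispensing after the review.
- Moving LSAS as well is optional. It would match the row order of Table 2-1, but Section 8.2 contains no LSAS criterion, so eligibility under that section does not need it. CGI-S can stay where it is, as its row in Table 2-1 is already below the review.

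The change needs a few bullets moved in one section, with the Visit 2 worksheet to match. It adds no assessment. The downside is that a few subjects found ineligible at Visit 2 will have been given the two scales before being turned away.
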